3. STUDY OBJECTIVES

The objectives of this study is to address the questions about the concerns of patients and their caregivers regarding quality of life and relapse after prisoner reentry into the community. To do this, we will examine an extended release vehicle (XR-NTX) as a comparative tool to treatment as usual.

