5.8 Premature Termination or Suspension of Study

This trial will use the University of Pennsylvania Center on Studies of Addiction Internal Data and Safety Monitoring Board (DSMB). There are no plans for interim analysis of safety data however the PI and DSMB will review safety data every 6 months and annually, as required by the protocol, or more often if necessary. Adverse experience and safety contrasts will be performed as indicated, in response to recommendations by the PI and DSMB.

5.9 Potential Problems and how they will be addressed:

5.9.1 Recruitment:

We will print brochures describing the study and will have access to all PPS units. Inmates meeting criteria for opioid dependence with physiologic features are usually easy to identify because they go into withdrawal shortly after entering the PPS. We will review recruitment information at weekly research meetings and consider increasing the number of staff or staff time available to identify study candidates if we fall behind. 2) Not meeting an 80% follow-up rate. [name] is working with NET Steps on the START study and has been highly effective but if we are not meeting goals, we will use the van that he uses to meet participants in the community for HIV studies led by [name]. 3) Difficulties within PPS. We will ask the Recovery Specialists, other PPS staff, [name], or the Commissioner for help if this occurs. 4) Illness of key staff members. Though we have no indication that such a problem will occur, other senior faculty could be called upon to manage the study. [name] . (PsyD) is a highly experienced Project Director who has had significant experience in managing other studies.

5.9.2 Dropout and Follow-up:

5.9.2.1 Locator Data Collection: A detailed contact sheet will be completed for all patients at baseline and updated at each subsequent assessment. We will ask patients to provide contact information on themselves and

three others (treatment programs, friends, relatives) with whom they are most likely to stay in contact, and also ask about places where they might be able to be contacted if we cannot locate them directly or via contacts. Research staff will ask for updates about changes in contact information at each assessment.

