12) Quality of Life: measured by the EuroQol (EuroQol Group, 1990), a standardized measure for describing and valuing health-related quality of life. It consists of two components: one that describes current health in five domains, by choosing one of three levels in each of five domains: mobility, self-care, usual activities, pain/discomfort, and anxiety/depression; and the other a visual analogue scale where patients rate their current global health state by choosing a number from a visual analogue scale that ranges from 0 to 100- where 0 represents the worst imaginable health and 100 is the best imaginable health. It was used in the cost-effectiveness study of short vs. longer-term buprenorphine-naloxone treatment for opioid addicted youth where it showed improvement with addiction treatment (Polsky et al, 2010), and will be done at baseline using the timeframe “when you entered the PPS”, and at 12 and 24 weeks using the timeframe “since your last assessment”.

13) Psychiatric Symptoms: measured by the Psychiatric Composite Score of the ASI and the Beck Depression Inventory (BDI; Beck et al, 1961) for 30 days prior to incarceration at baseline and at 12 and 24 weeks after reentry.

14) HIV Drug and Sex Risk: Done at baseline and at 12 and 24 weeks using the Risk Assessment Battery (RAB), a self-report of drug use and injection and sex risk behaviors (Navaline et al, 1994; [name] et al, 2001) that will assess HIV risk over the 12 weeks prior to incarceration at baseline and the past 12 weeks at each follow-up. The RAB has 38 closed end items that cover issues of substance use including frequency, needle sharing and cleaning, and condom use. Responses on the RAB have been equivalent to those collected by

personal interview, and scores were able to discriminate between cocaine and opioid abusers as well as those who converted to HIV+ from those who remained HIV negative ([name] et al, 2001).

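### EuroQol is described as current health but asked over recall periods, and the follow-up period is undefined, so quality of life lacks a common window and a current pre-release score

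*Combined protocol and SAP*

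**What the plan says.** Section 8.1 item 12 gives the EuroQol two parts. The first is "one that describes current health in five domains, by choosing one of three levels in each of five domains". In the second, "patients rate their current global health state" on a 0 to 100 visual analogue scale. The same item then sets the timeframes: the instrument "will be done at baseline using the timeframe “when you entered the PPS”, and at 12 and 24 weeks using the timeframe “since your last" (the cut final word is assessment).

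Section 7 schedules EuroQol at screening (7.1), month 3 (7.3), month 6 (7.4) and any withdrawal visit (7.5). Screening takes place in jail and comes before randomization, which is listed under 7.2. Section 4.1 adds brief assessments at months 1, 2, 4 and 5.

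The Section 3 objective is to "address the questions about the concerns of patients and their caregivers regarding quality of life and relapse after prisoner reentry into the community", and quality of life is listed first of the ten secondary outcomes in 3.1.2. Section 13.4 analyses it with a linear mixed model containing group, time, their interaction and any necessary covariates. Section 5.9.1 remarks that inmates with physiologic opioid dependence are "usually easy to identify because they go into withdrawal shortly after entering the PPS".

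**The concern.** A five-domain profile with one level per domain, and one 0 to 100 rating, describe a state at a point in time. Item 12 says as much, then asks for them over a stretch of time. A participant who was protected by medication, relapsed and was rearrested within that stretch has no single correct answer.

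Two things are at stake. First, the follow-up scores may refer to different periods for different participants, and at month 3 may include time before release. Second, the only baseline is a recollection of health on arrival in jail, a moment close to withdrawal by the protocol's own account. No score records how participants were when they were about to be released. A change from baseline would then combine a real change in health with a change in what was asked.

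**Working it through.** The plan gives no sample size, standard deviation or effect size for EuroQol, so there is no stated figure to reproduce. The check sets the wording against the schedule and sizes the ambiguity.

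**Step 1: concept against timeframe (8.1 item 12).**

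| Time point | What the instrument is said to describe | What is asked |
|---|---|---|
| Screening | current health | health on entering the jail |
| Week 12 | current health | period since the last assessment |
| Week 24 | current health | period since the last assessment |

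No row matches. The withdrawal-visit EuroQol has no timeframe in item 12.

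**Step 2: what the last assessment is.** Two readings are open.

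- *Reading A, the previous EuroQol.* The month-3 window starts at screening, in jail. The incarceration question added to the ASI (8.1 item 5) uses similar wording. Since the ASI is also scheduled only at screening, month 3 and month 6, that question must reach back to the previous ASI to cover follow-up fully.
- *Reading B, the last visit attended.* Section 4.1 calls the contacts at months 1, 2, 4 and 5 assessments, so the month-3 window would normally start at month 2.

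**Step 3: Reading A, week 12 counted from release.** Let w be the weeks from the screening EuroQol to release. The documents do not give w; the values here are assumptions. Jail share of the month-3 window = w/(w + 12):

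- w = 2: 2/14 = 14%
- w = 4: 4/16 = 25%
- w = 8: 8/20 = 40%

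Over a wider assumed range in days, g/(g + 84) gives 7/91 = 8% at 7 days and 180/264 = 68% at 180 days.

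**Step 4: Reading A, week 12 counted from first injection (Group A).** Section 5.5 leaves the visit schedule unchanged if a Group A participant is held for up to 30 days from the first injection. Assuming screening 14 days before injection and a 30-day hold, the share is (14 + 30)/(14 + 84) = 44/98 = 45%. Group B is injected after release, so on this clock the jail share could differ by arm. Item 12 does not state the clock. Item 13, on psychiatric symptoms, counts 12 and 24 weeks from reentry.

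**Step 5: Reading B.** With nominal visit times, a participant who attended month 2 has a window of 12 − 8 = 4 weeks. One who missed month 2 but attended month 1 has 12 − 4 = 8 weeks. One who missed both goes back to baseline. There is no jail time if visits are counted from release and the participant is not rearrested, but the window length depends on attendance, which comes after randomization and may differ by arm.

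**Step 6: effect of the recalled baseline.** Write A0 and B0 for the arm means at screening, and A1 and B1 at follow-up. The group-by-time contrast is (A1 − A0) − (B1 − B0). The screening score is taken before randomization with the same wording in both arms, so A0 and B0 have the same expectation and the contrast has expectation A1 − B1. The baseline frame therefore does not by itself bias the comparison. The within-arm change A1 − A0 does carry the shift from jail-entry recall to follow-up recall, and so does the time term.

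**The case against.** The strongest reply is that the baseline frame looks deliberate. Section 8.1 also asks about the period before incarceration for the TLFB, psychiatric symptoms, the RAB, employment and non-study medical services. A rating made in custody describes confined life, in which an item such as usual activities means something different. This stands in part: a reference point outside custody is a legitimate choice, so the jail-entry item need not be removed. It does not explain why EuroQol alone is anchored on entry itself rather than on a period before it, nor does it defend the follow-up wording.

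A second reply is that the jail share depends on Reading A, on an assumed gap, and on how respondents summarise an interval. That is correct. The percentages illustrate the ambiguity and do not estimate a bias. Reading B removes the jail time but leaves a window set by attendance.

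A reader might go further and infer that quality of life after reentry is not measured at all. The schedule does not support this. On either reading the month-6 window starts at month 3 or later, which is normally community time, and month 3 lies at least partly after reentry. A reader might also infer that improvement from baseline would mainly be recovery from withdrawal and would be presented as benefit. That the recalled score reflects withdrawal is a reasonable inference from 5.9.1, but no data show its size, and Section 13.4 plans comparisons between groups, not claims from within-arm change. Nor does 13.4 name baseline EuroQol as a covariate, so a loss of precision from that source would depend on a step not specified.

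**Conclusion.** The point holds as a measurement defect in one secondary outcome. Item 12 is inconsistent with its own description of the instrument, and the follow-up window has at least two readings, neither of which gives every participant the same defined period. Quality of life after reentry is measured, but not as a current state over a common window. No current health state is recorded before release, so change from baseline and the time term are hard to interpret.

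The size is conditional. Under Reading A with week 12 counted from release, the jail share at month 3 is 14%, 25% or 40% for assumed gaps of 2, 4 or 8 weeks. Under Reading B the nominal window is 4 weeks, and 8 or more where visits are missed. The between-arm contrast is not biased by the recalled baseline alone. It could be affected if window length, or jail time within the window, differs by arm; the documents do not show whether that will happen. The primary outcome is untouched.

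**What to change.** In 8.1 item 12:

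- Ask EuroQol as health today at weeks 12 and 24.
- State that both visits are counted from release in both arms, in line with item 13. Same-day wording alone does not settle this. If visits ran from injection, a Group A participant held 30 days would be rated 84 − 30 = 54 days after release, and a Group B participant injected on day 7 would be rated 84 + 7 = 91 days after release.
- Record a same-day score at screening and name it in 13.4 as the baseline value.
- Keep the jail-entry recall, if wanted, as a separate descriptive item outside the mixed model.
- Give the withdrawal-visit EuroQol the same timeframe.

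The instrument and visits stay the same and no sample size changes. The cost is revised CRF wording and a few extra questions at screening. The trade-off is that follow-up scores will reflect one day instead of an interval, and the screening score will reflect health in custody, which is why the jail-entry item may be worth keeping beside it.

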8.2 LABORATORY PROCEDURES/MEASURES

8.2.1 Clinical Laboratory Tests

- 1) The study will use historical data if available from PPS. The study will use the OraSure Rapid oral test (swab) for HIV if study performs test. Study screens will be confirmed via laboratory if positive.
- 2) CBC, Blood Chemistry, HBV and HCV tests. Will use historical data if < than 60 days old. We will use PPS medical contractor to draw blood if >60 days.
- 3) Liver Tests (ALT, AST, GGT). Will use historical data if < than 60 days old. Will use PPS medical contractor to draw blood if >60 days.
- 4) Will use historical data from PPS at screen. PPD tests will be performed at screen by the PPS medical contractor if status is unknown.
- 5 Historical Urine or blood pregnancy test used at screening if < 60 days old, but will be readministered at baseline before the administration of Vivitrol, and then urine or blood pregnancy dip tests monthly after reentry throughout the study.

8.2.2 Specimen Preparation and Handling

All rapid test kits will be labeled with the patient's ID number before testing and reading. The kits come one kit per package. Will be stored in locked cabinets before use.

9. DATA MANAGEMENT AND CASE REPORT FORMS (CRFs)

[name] and [name] will construct a web-based system modeled on ones they developed for other studies. Data will be password protected and entered on desktop or laptop computers by research staff. Only study numbers will identify subjects, and data linking subjects to numbers will be kept in a locked cabinet in a secure office at PPS that is designated for that purpose. The system will be programmed with range checks and stops that will not let data entry proceed if important pieces of information are inconsistent or missing. Investigators will be alerted to problems with missed assessments or other protocol deviations. Data will be backed up daily and secured using password protected Login IDs.

Study data will be collected via the web-based system. A complete, cleaned and de-identified copy of the dataset will be made available upon request within a month of receiving a request but not more than nine months from the end of the final year of funding. The dataset will be entered into the NIH system as was done with the NIDA study of buprenorphine-naloxone for opioid addicted youth ([name] et al, 2008) and with other studies in the Clinical Trails Network.

9.1 Data Handling & Record Keeping

9.2 Confidentiality: Subject visits are conducted in a private study office. Interviews are monitored visually by prison security personnel who are located outside of the room, but will not be able to hear the interviews. Source documents collected from the interviews will be kept in a locked file cabinet within a locked room in the study office. Subject data will be kept confidential and managed according to the HIPAA requirements that include a signed authorization informing the subject of what protected health information (PHI) will be collected; who will have access to that information and why; who will use or disclose that information; and their rights to revoke authorization for use of their PHI. If a subject revokes authorization to collect or use PHI, the investigator retains the ability to use information collected prior to the revocation of authorization. For subjects who revoke authorization to collect or use PHI, attempts will be made to obtain permission to collect vital status (i.e. that the subject is alive) at the end of their scheduled study period.

9.3 Source Documents: Source data include all information, original records of clinical findings, observations, or other activities in a clinical trial necessary for the reconstruction and evaluation of the trial. Source data are in documents such as: hospital records, clinical and office charts, laboratory notes, memoranda, subjects' diaries or evaluation checklists, pharmacy dispensing records, recorded data from automated instruments, copies or transcriptions certified after verification as being accurate and complete, microfiche, photographic negatives, microfilm or magnetic media, x-rays, subject files, and records kept at the pharmacy, at laboratories, or at medico-technical departments involved in the clinical trial.

9.4 Case Report Forms (CRFs): These include all primary data collection instruments and are entered and accessed through the web-based data management system. The system will be programmed so that each form is validated to check for blank fields and inconsistencies.

9.5 Records Retention: Source documents will be retained for at least 7 years after data lock.

10. ASSESSMENT OF SAFETY

10.1 Potential XR-NTX (Vivitrol®) Risks:

10.1.2 Injection Site Reactions:

XR-NTX is administered as a gluteal intramuscular injection and inadvertent subcutaneous injection may increase the likelihood of severe injection site reactions. To reduce this possibility, each needle provided in the XR-NTX kit is customized and no other needle can be used. Because needle length may not be adequate in every patient because of body habitus (e.g. severe obesity that reduces the chances for intramuscular administration), each participant will be assessed prior to injection to assure that needle length is adequate and those whose subcutaneous tissue is so thick that the needle is unlikely to reach the muscle will not be enrolled. Patients will be educated to report concerning injection site reactions to the attention of the clinician and research staff.

Injection site reactions are the most common AEs and have been reported in 50% of the placebo group and 69% of the 380 mg Vivitrol® group in alcohol treatment studies. They include pain, tenderness, induration, swelling, erythema, bruising, or pruritus and typically resolve in 1-3 days but can be severe. In clinical trials for alcohol dependence one patient developed hardening of tissue at the injection site that continued to enlarge after 4 weeks and required surgical excision. In the post-marketing period additional cases of injection site reactions with induration, cellulitis, hematoma, abscess, sterile abscess, and necrosis have been reported. In some cases, these problems required surgical intervention including debridement of necrotic tissue with some resulting in significant scarring. These cases occurred primarily in female patients. A physician will examine patients exhibiting abscess, cellulitis, necrosis, or extensive swelling to determine if referral to a surgeon or other specialist is needed.

10.1.3 Unintended Precipitation of Opioid Withdrawal:

XR-NTX will precipitate or exacerbate opioid withdrawal unless the patient has been opioid-free for 7-10 days, which is expected to be the case in all but a very few potential study candidates. An opioid negative urine test, drug use history, psychiatric interview and observation for signs and symptoms of current opioid use or withdrawal will be done prior to the first naloxone challenge and the challenge will not be done unless the person appears to be free of physiologic opioid dependence. The absence of current physiologic dependence will be confirmed by self-report, clinical observations, and a score of <5 on a COWS that is administered 15 -30 minutes after receiving 0.4 - 0.8 mg naloxone I.M. Clonidine 0.2 to 0.6 mg will be used to suppress withdrawal if it occurs, and blood pressure will be checked every 15 minutes until there is no evidence of hypotension and/or withdrawal over the next 45-60 minutes. Similar procedures will be followed prior to subsequent XR-NTX injections, however the naloxone challenge will not be re-administered if the clinical situation clearly indicates the absence of relapse. Patients that have relapsed will be referred to the most appropriate available treatment, as previously described.

10.1.4 Opioid Overdose From an Attempt to Overcome Opioid Blockade: Patients will be told that attempting to overcome the XR-NTX blockade by administering large amounts of opioids is dangerous and may result in fatal overdose.

10.1.5 Liver Toxicity: The most serious adverse effect associated with naltrexone is hepatocellular injury, which has almost always been associated with oral doses of 1400 to 2100 mg per week. These doses produce much greater naltrexone exposure than the 380-mg/monthly doses from a XR-NTX injection. At oral doses below 600 mg/week only relatively minor changes in liver tests were reported and these were not clearly attributed to naltrexone. In addition, a study of actively drinking alcoholics who received a once-monthly injection found no evidence of liver toxicity. This study enrolled 624 patients (68% male; median age 44), and randomly assigned them to XR-NTX 380 mg (n=205), XR-NTX 190 mg (n=210) or placebo (n=209). There were no significant differences in ALT, AST, or bilirubin levels between study groups at any post-baseline assessment; GGT in the 380 mg group was lower compared with placebo at weeks 4, 8, 12, and 20 and high (> 3 times upper limit of normal) liver chemistry tests (LCTs) and hepatic-related adverse events were infrequent in all treatment groups. In a subset of patients who were drinking heavily throughout the study, or who were obese or taking NSAIDs, there was no increase in frequency of high LCTs or hepatic-related adverse events in those receiving either dose of Vivitrol® (Lucey et al, 2008).

10.1.6 Hepatic Impairment: XR-NTX pharmacokinetics has not been shown to alter hepatic states in patients with mild to moderate hepatic impairment, and dose adjustment is not required for these individuals. However they have not been evaluated in subjects with severe hepatic impairment, thus individuals with severe renal disease will be excluded from the study. *Gastrointestinal Effects:* The most common gastrointestinal AEs are nausea (11% placebo group; 33% XR-NTX 380 mg group) and vomiting (6% placebo group; 14% XR-NTX 380 mg group).

10.1.7 Renal Impairment: A pharmacokinetic analysis indicated that mild renal insufficiency (creatinine clearance of 50-80 mL/min) had little or no influence on Vivitrol® pharmacokinetics and that no dosage adjustment is necessary. XR-NTX pharmacokinetics have not been evaluated in subjects with severe renal insufficiency thus these individuals will not be included in this study.

Gender: In a study of healthy subjects (n=18 females; 18 males), gender did not influence the pharmacokinetics of XR-NTX.

10.1.8 Age and Race: The pharmacokinetics of XR-NTX has not been evaluated in the geriatric population, nor has the effect of race on pharmacokinetics.

10.1.9 Drug Interactions: The metabolic pathway of naltrexone suggests that it does not appear to have significant interactions with other drugs but studies evaluating interactions have not been performed.

10.1.10 Reversal of Blockade for Pain Management: In an emergency situation, suggestions for pain management are regional anesthesia or non-opioid analgesics. If opioids are required for anesthesia or analgesia, patients should be continuously monitored in an anesthesia care setting by persons not involved in the conduct of the surgical or diagnostic procedure. The opioid therapy must be provided by persons specifically trained in the use of anesthetic drugs and the management of respiratory effects of potent opioids, specifically the establishment and maintenance of a patent airway and assisted ventilation.

10.1.11 Depression and Suicidality: In controlled trials among patients with alcohol dependence, AEs of a suicidal nature (suicidal ideation, attempts, completed suicides) were infrequent overall, but more common in patients treated with XR-NTX than placebo (1%). In some cases, the suicidal thoughts or behavior occurred after medication discontinuation but were in the context of an episode of depression that began while the patient was on the study drug. Two completed suicides occurred in alcohol treatment studies, both in patients treated with XR-NTX Depression-related events were also more common in patients treated with XR-NTX than in those on placebo (1%).

10.1.12 Contraindications: Patients should not receive XR-NTX if they are taking opioid analgesics; have current opioid dependence, are in opioid withdrawal, failed a naloxone challenge, or have a positive urine

screen for opioids; exhibited hypersensitivity to naltrexone, PLG, carboxymethylcellulose, or any other components of the diluent; or have acute hepatitis or liver failure.

10.1.13 Eosinophilic Pneumonia: In clinical trials, there was one diagnosed case and one suspected case of eosinophilic pneumonia. Both cases required hospitalization and resolved with antibiotics and corticosteroids. Should a person receiving XR-NTX develop progressive dyspnea and hypoxemia, the diagnosis of eosinophilic pneumonia should be considered.

